## **10.9.** Safety-Related Stopping Criteria

#### **10.9.1.** Bleeding Events

Any bleeding event reported as Bleeding Academic Research Consortium (BARC) 3 or greater will pause enrollment and the event will be reviewed by the Investigator and Medical Monitor. Following review, the event may trigger unblinding, study stop, or the study may resume (following approval by health authorities and IECs/IRBs in accordance with applicable country-specific regulations).

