#### 6.3. Dosage and Administration

All enrolled subjects will receive a single oral dose of study treatment at each Treatment Visit, for a total of 3 doses of study treatment. Each subject will receive a single administration of each dose strength. Temanogrel doses to be administered in Stage A will be 60 mg (3 temanogrel capsules and 3 placebo capsules) or 120 mg (6 temanogrel capsules). Placebo doses will be administered as 6 placebo capsules. Selection of doses for Stage B will be based on the results from Stage A. Refer to Section 6.4 for further details related to treatment assignment.

Study treatment will be administered in a blinded fashion to the subjects. Study treatment administration will be performed by the Investigator or a qualified designee (eg, nurse). Study treatment will be administered orally with water (a maximum of 250 mL should be targeted; however, additional water may be ingested if required to administer the full dose of medication). A mouth check will be performed by the qualified designee to ensure that the subject has swallowed the study treatment. The date and exact clock time of each dosing will be recorded.

Study treatment requirements, dispensation, administration, destruction, and study staff roles will be further defined in a pharmacy manual.

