#### 6.3.2. Dose Interruptions

Subjects will be administered a single dose of study treatment at each Treatment Visit. Therefore, there will not be any dose interruptions.

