## 8.4. Premature Termination of the Study or a Study Site

The Sponsor has the right to terminate this study at any time. Reasons for terminating the study may include, but are not limited to, the following:

- The incidence or severity of adverse events in this or other studies indicates a potential health hazard to subjects
- Subject enrollment is unsatisfactory
- Upon request of Health Authorities

The Sponsor will notify the Investigator if the study is placed on hold or if the Sponsor decides to discontinue the study. Health authorities and Independent Ethics Committees (IECs)/ Institutional Review Boards (IRBs) will be informed about the termination of the study in accordance with applicable regulations.

The Sponsor has the right to replace a study site at any time. Reasons for replacing a study site may include, but are not limited to:

- Excessively slow recruitment
- Poor protocol adherence
- Inaccurate or incomplete data recording
- Non-compliance with the ICH guideline for GCP

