## 9. STUDY PERIODS

### 9.1. Screening

The Screening period is to occur up to 28 days prior to Treatment Visit 1 (Day –28 to 1). For details of the study Screening and enrollment see the Schedule of Assessments (Appendix 1). Potential subjects will provide written informed consent before any study-specific procedure is performed. Eligible subjects meeting all inclusion/exclusion criteria requirements may be enrolled.

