## 9.2. Treatment Visits

Randomization can occur after confirmation of all inclusion and exclusion criteria at Check-in prior to the planned administration of study treatment on Treatment Visit 1.

Each subject will participate in 3 Treatment Visits, which will each be separated by a Washout Period of at least 72 hours and up to approximately 7 days between study treatment administrations. When possible, it is preferred to schedule Treatment Visits with the minimum possible Washout Period between visits. For each Treatment Visit, subjects will be admitted to the clinic at approximately the same time of the day (between 0800 and 1200 hours). A schematic of Treatment Day assessments and procedures is provided in Appendix 2. Refer to the Schedule of Assessments (Appendix 1) for additional details on study assessments and procedures.

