#### 10.2.8. Pregnancy Testing

A serum pregnancy test for beta-human chorionic gonadotropin ( $\beta$ -hCG) will be performed on WOCBP at screening to determine eligibility and at each Treatment Visit. At each treatment visit, urine pregnancy tests ( $\beta$ -hCG) will be performed, and a negative result is required to be documented, prior to administration of study treatment. The results of the serum pregnancy test

at each Treatment Visit are not required prior to dosing. If at any point there is a case of a positive urine  $\beta$ -hCG test, the subject will have study treatment interrupted. If the serum test confirms positive, the subject will be discontinued from the study treatment and all the necessary follow up will be conducted as per Section 10.8.6. If the serum test is negative, the subject may resume study treatment.

At Treatment Visit 1, WOCBP will also be provided with a urine pregnancy test that is to be taken at home prior to the subject's Follow-Up visit on the same day of the Follow-Up visit. During the first Treatment Visit subjects will receive adequate training on the use of the home pregnancy test and will be informed on how to properly communicate the results of their test. If the result of the home pregnancy test is positive, subjects will be required to undergo a serum pregnancy test. If the serum test confirms positive, all necessary follow-up will be conducted as per Section 10.8.6. If the serum test is negative, no further follow-up is required.

Women who are surgically sterile or who are postmenopausal are not considered to be of child-bearing potential. Postmenopausal is defined as 12 consecutive months with no menses without an alternative medical cause.

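### After a BARC 3+ bleed, Section 10.9.1 expressly pauses only enrolment; no sentence pauses dosing of subjects already randomised

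*Combined protocol and SAP*

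**What the plan says.** Section 10.9.1 (Bleeding Events), under the safety-related stopping criteria, has two sentences. The first says that a bleed of BARC grade 3 or higher "will pause enrollment and the event will be reviewed by the Investigator and Medical Monitor". The second says that after the review "the event may trigger unblinding, study stop, or the study may resume", with resumption subject to approval by health authorities and ethics committees. Neither sentence mentions dosing.

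Elsewhere the protocol uses enrolment for entry into the study. In Section 9.1, "Eligible subjects meeting all inclusion/exclusion criteria requirements may be enrolled". Section 6.3 then sets the regimen: "All enrolled subjects will receive a single oral dose of study treatment at each Treatment Visit, for a total of 3 doses". It makes no exception for a safety pause.

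Doses are 72 hours to about 7 days apart. Section 9.2 adds that, where possible, "it is preferred to schedule Treatment Visits with the minimum possible Washout Period between visits".

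Three other provisions could stop dosing. Section 8.1 lists reasons for which a subject's treatment may be stopped, including an adverse event or a physician's decision. Section 8.4 lets the Sponsor terminate the study and foresees a hold: "The Sponsor will notify the Investigator if the study is placed on hold". Section 12.5 lets an investigator depart from the protocol without prior approval to remove an immediate hazard.

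**The concern.** A stopping rule should tell a site what to do on the day it is triggered. This one tells the site to stop entering subjects. It does not tell a site with a subject due for the second or third visit whether to dose, and the regimen sentence in Section 6.3 says to dose. The literal reading is therefore the less safe one.

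The protocol is explicit where it wants treatment to stop for other reasons. After a positive urine pregnancy test (Section 10.2.8), "the subject will have study treatment interrupted". A new hand ulcer (Section 10.8.2) ends both treatment and participation. The liver rule in Section 10.9.2, directly after the bleeding rule, is framed around stopping study treatment. Only the major-bleed rule is framed around enrolment.

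At stake is giving a drug with antiplatelet action to subjects in mid-sequence while a major bleed is being reviewed. Section 11.8.2.1 accepts that single oral doses in this study might raise bleeding tendency. Aspirin is permitted (exclusion criterion 13), and Stage B doses may reach 240 mg.

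**Working it through.** The plan gives no figure for doses at risk during a review, so this is a count from its design.

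**Inputs**
- Six sequences, equally allocated: ABC, ACB, BAC, BCA, CAB, CBA, where C is placebo (Section 6.4).
- Interval between doses: 3 days at minimum, about 7 days at maximum (Section 9.2).
- Length of the review: not stated, so a range is assumed.

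**Active doses still due**
- Each period is active in 4 of the 6 sequences: 4/6 = 0.67.
- After dose 1, two doses remain. Four sequences have 1 active dose left and two have 2: (4×1 + 2×2)/6 = 1.33.
- After dose 2, one dose remains. It is active in four sequences and placebo in two: 4/6 = 0.67.

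**When they fall due**
- Just past dose 1: days 3 and 6 at minimum washout; about days 7 and 14 at maximum.
- Just past dose 2: day 3 at minimum; about day 7 at maximum.

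**Mean active doses given during a review of R days, per subject, if dosing continues**

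| Review length R | Just past dose 1: min / max washout | Just past dose 2: min / max washout |
|---|---|---|
| under 3 days | 0 / 0 | 0 / 0 |
| 3 days | 0.67 / 0 | 0.67 / 0 |
| 7 days | 1.33 / 0.67 | 0.67 / 0.67 |
| 14 days or more | 1.33 / 1.33 | 0.67 / 0.67 |

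At minimum washout both remaining doses have been given by day 6, so a longer review adds nothing. Days count from the subject's last dose. A subject already 2 days into a 3-day washout when the bleed occurs is due again in 3 − 2 = 1 day, so a short review can also overlap a dose.

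**Effect of a pause on the stated duration.** The 47-day maximum reproduces as 28 days of screening + 2×7 days of washout + 5 days to the latest follow-up = 47. A subject already on the maximum schedule has no slack, so any pause in dosing takes that subject past the limit.

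**What cannot be computed.** No accrual rate is given, so the number of subjects in mid-sequence when a bleed occurs is unknown. The table counts doses and does not measure bleeding risk.

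**The case against.** The strongest reply is that Section 10.9.1 already implies a full halt. It sits under stopping criteria, a study that never stopped cannot resume, and needing authority and ethics approval fits a study-wide halt better than a recruitment pause. This stands as evidence of intent. A reader might infer from the first sentence that the sponsor chose to dose through a major bleed; the second sentence tells against that. What remains is that sites must infer the halt.

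A reader might also take Section 6.3.2, which says "there will not be any dose interruptions", as an instruction to keep dosing. It is not one. It describes a design with one dose per visit, and Section 10.2.8 already interrupts treatment despite it. The argument rests on Section 6.3 alone.

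The other routes also narrow the gap. Most BARC 3+ events would probably be serious adverse events, reported within 24 hours, so the Sponsor would know quickly and could call a hold. The investigator treating the affected subject could stop that subject's treatment. These routes may well be used. But each needs a separate decision, none is tied to the BARC trigger, and an investigator at another site whose own subjects are well would have to judge whether a distant bleed is an immediate hazard under Section 12.5.

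Finally, the risk may be low. Section 1.2 reports no bleeding events in healthy subjects after single oral doses alone up to 320 mg, and expects a bleeding risk well below that of standard antiplatelet agents. Bleeding-prone subjects are excluded. This limits the point's weight. However, a BARC 3+ event is when that expectation comes into question.

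**Conclusion.** The point holds as a defect in the wording of a stopping rule. The automatic action covers enrolment only, no sentence pauses dosing, and Section 6.3 read literally leaves the remaining doses on schedule. Per subject, that is a mean of 1.33 active doses after dose 1 or 0.67 after dose 2, due from 3 days after the last dose. How many would be given depends on the assumed review length. The absolute risk is probably small.

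The documents do not show that continued dosing was intended, or that any subject was dosed during such a review. The October 2022 Note to File records that enrolment was terminated after the decision of 25 August 2022 and that the database was locked on 13 October 2022. The correction therefore matters for the protocol as written and for any reuse of its text.

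**What to change.** 1. **Section 10.9.1**, first sentence: say that the event *will pause enrollment and further dosing of all randomized subjects pending review of the event by the Investigator and Medical Monitor; the subject with the event will receive no further study treatment unless that review supports it*. Keep the second sentence.
2. **Section 6.3**, three-dose sentence: add *unless dosing is paused under Section 10.9.1*.
3. **Washout limit of about 7 days** (Synopsis, Sections 3, 3.2.3 and 9.2, Appendix 1 footnote a): allow it to be exceeded in that case.
4. **Maximum duration of 47 days** (Synopsis and Section 3): allow the same.

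That is nine statements (1 + 1 + 5 + 2). If a full halt was always meant, the edits only state it.

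The cost arises only after a BARC 3+ event. Some washouts and study durations lengthen, medication restrictions (which run to the Follow-Up Visit under Section 5.4) last longer, and some subjects may not complete all three periods. Section 8 already allows such subjects to be replaced, and Section 6.4 puts the replacement in the same sequence. A longer washout should not add carryover, because Section 3.2.3 states that 72 hours is enough for elimination.

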### **10.9.2. Drug-Induced** Liver Injury

Discontinuation of study treatment for an individual subject should be considered if any of the following occur:

- ALT or AST  $> 8 \times ULN$
- ALT or AST  $> 5 \times$  ULN for more than 2 weeks
- ALT or AST > 3 × ULN and total bilirubin (TBL) > 2 × ULN or International Normalized Ratio (INR) > 1.5
- ALT or  $AST > 3 \times ULN$  with the appearance of fatigue, nausea, vomiting, right upper quadrant pain or tenderness, fever, rash, and/or eosinophilia (> 5%)

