On Day 1, subjects will be admitted to the clinic for Treatment Visit 1. After Check-in assessments including blood sampling for clinical laboratory assessments, PK, and biomarkers, subjects will acclimatize for at least 20 minutes in a temperature-controlled room (23 [ $\pm$  1]°C) followed by Predose digital blood flow assessments for 5 minutes at room temperature based on simultaneous collection of temperature and perfusion data using infrared (IR) thermography and laser speckle contrast imaging (LSCI), respectively. After study treatment administration, subjects will undergo re-acclimatization for at least 20 minutes, followed by Postdose assessments. Postdose assessments will start 45 ( $\pm$  5) minutes after dosing with digital blood flow assessments performed once again for 5 minutes at room temperature. A cold challenge will then be conducted by immersing the hands in a temperature-controlled water bath  $(15 [\pm 1]^{\circ}C)$ for 1 minute, followed by post-cold challenge digital blood flow assessments that will start  $30 (\pm 10)$  seconds after the end of the cold challenge and last for 30 minutes. Blood samples for clinical laboratory assessments, PK, and biomarkers will be collected again after post-cold challenge digital blood flow assessments are complete. Subjects will be discharged from the study unit once all planned Postdose assessments have been completed. For Treatment Visit 2 and Treatment Visit 3, subjects will return to the clinic at approximately the same time of the day as for Treatment Visit 1 (between 0800 and 1200 hours) and will undergo the same assessments as for Treatment Visit 1. A schematic of Treatment Day assessments and procedures is provided in Appendix 2. Refer to the Schedule of Assessments (Appendix 1) for additional details on study assessments and procedures. A Follow-Up Visit will occur 4 ( $\pm$  1) days after administration of final study treatment for a total study duration of 10 to 47 days.

Following the double-blinded conduct of Stage A, the Sponsor will conduct an unblinded evaluation of the efficacy and safety results prior to proceeding to Stage B. In Stage B, 2 single doses of temanogrel (doses to be determined after review of Stage A data, but not exceeding 240 mg) and placebo are planned to be evaluated with a study design identical to Stage A.

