#### **3.2.2.** Study Population

The study population consisting of subjects with SSc-RP was chosen as representative of the target population. However, subjects with active (or recurrent) skin ulcerations were excluded to avoid the additional burden associated with performing cold challenges, as well as potentially confounding the blood flow assessments. Subjects with advanced multiorgan disease, in particular gastrointestinal dysfunction, have been excluded due to the potential for delayed and/or poor absorption of temanogrel. Although embryo-fetal development studies have not been completed for the temanogrel program, women of child-bearing potential (WOCBP) will be included in the study population. Considering SSc occurs in women approximately 5 to 10 times more frequently than in men (Bergamasco 2019, Lo Monaco 2011), it would be difficult to effectively meet study objectives and perform a representative assessment without the inclusion of WOCBP in this population. In accordance with FDA Guidance for Industry, M3(R2)Nonclinical Safety Studies for the Conduct of Human Clinical Trials and Marketing Authorization for Pharmaceuticals (FDA 2010), inclusion of WOCBP is acceptable because the study is of short treatment duration (less than 2 weeks). In addition, participants who are of child-bearing potential will practice effective control of pregnancy risk and will undergo urine pregnancy testing prior to treatment administration on each Treatment Visit day and a home urine pregnancy test will be administered as part of the final Follow-Up Visit. Serum pregnancy testing will be performed prior to study enrollment and at each Treatment Visit.

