## 9.3. Follow-Up/End of Study

Subjects will have one Follow-Up Visit via phone call, and preferably via teleconference,  $4 (\pm 1)$  days after the completion of Treatment Visit 3 to assess for adverse events, update concomitant medications, and if applicable, communicate the results of the home pregnancy test (Section 10.2.8). For each subject, study participation is completed once the Follow-Up Visit has been conducted. The End of Study Date is the date when the last subject completes his/her final Follow-Up Visit.

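### On the planned schedule, a rise starting after dose 1 cannot meet the liver criterion of more than 2 weeks above 5 × ULN while a dose is left to withhold

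*Combined protocol and SAP*

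**What the plan says.** Section 10.9.2 opens with "Discontinuation of study treatment for an individual subject should be considered if any of the following occur" and lists four criteria for ALT or AST:

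- above 8 × ULN
- above 5 × "ULN for more than 2 weeks"
- above 3 × ULN with total bilirubin above 2 × ULN or INR above 1.5
- above 3 × ULN with listed symptoms or eosinophils above 5%

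Only the second has a duration.

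Treatment is three single doses (Section 6.3). Visits are "separated by a Washout Period of at least 72 hours and up to approximately 7 days between study treatment administrations", and where possible "it is preferred to schedule Treatment Visits with the minimum possible Washout Period between visits" (Section 9.2). Section 3.2.2 states that "the study is of short treatment duration (less than 2 weeks"). Section 3 gives a "total study duration of 10 to 47 days".

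Chemistry, hematology and coagulation are drawn at Check-in and Postdose of every Treatment Visit, and none is scheduled at Follow-Up (Appendix 1). Samples go to a central laboratory. The Investigator must review and document the reports and should repeat clinically significant values (Section 10.8.4). No deadline links that review to the next dose. By contrast, for the urine pregnancy test in women of child-bearing potential, "a negative result is required to be documented, prior to administration of study treatment" (Section 10.2.8).

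**The concern.** A stopping criterion is useful only if it can be met while there is treatment left to stop. A requirement of more than 2 weeks suits continuous dosing. Here the whole dosing course is planned to take about 2 weeks at most, and the preferred schedule takes 6 days.

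At stake is one further dose, dose 3, in a subject whose transaminases rose after dose 1 and reached a level that the plan itself treats as a reason to consider stopping. Section 1.2 says subjects are not expected to gain any significant health benefit, so little weighs in favor of giving that dose. Endpoints and their analysis are not involved.

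**Working it through.** **Inputs.** Gap between doses: 3 to about 7 days (Section 9.2). Doses: 3, so 2 gaps (Section 6.3). Screening: up to 28 days (Section 9.1). Follow-Up: 4 ± 1 days after the last dose (Section 3). Duration in the criterion: more than 14 days (Section 10.9.2).

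**1. The plan's own figure.**
- Maximum: 28 + 2 × 7 + 5 = 47 days elapsed.
- Minimum: dose 1 on Day 1, dose 3 on Day 1 + 2 × 3 = Day 7, Follow-Up on Day 7 + 3 = Day 10. That is 10 days counting the first day, or 9 elapsed.

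Both ends of the stated range are recovered. The stated maximum therefore implies 47 − 28 − 5 = 14 days from dose 1 to dose 3.

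**2. Time available before the last dose.** Dose 1 to dose 3 is 2 × 3 = 6 to 2 × 7 = 14 days. A rise that starts after dose 1 has lasted less than 6 days (shortest schedule) to less than 14 days (longest) when dose 3 is given. The criterion needs more than 14.

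**3. Sensitivity to longer gaps.** With a gap of g days, the rise must start within 2g − 14 days of dose 1. Gaps above 7 days are assumed values.

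| Gap g (days) | Dose 1 to dose 3 (days) | Latest start after dose 1 (days) |
|---|---|---|
| 7 | 14 | 0 |
| 7.5 | 15 | 1 |
| 8 | 16 | 2 |

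**4. What scheduled samples can show.** The Visit 1 Postdose sample follows 45 ± 5 minutes of waiting, then 5 + 1 + 0.5 + 30 minutes of assessments and cold challenge. That is 76.5 to 86.5 minutes after dosing. I assume this is too early for a rise caused by dose 1, which would then first be seen at Visit 2 Check-in. From there:
- Dose 3 is 3 to about 7 days away, so the criterion falls short by 14 − 7 = 7 to 14 − 3 = 11 days.
- Counted from that sample, it is met only more than 7 to 11 days after dose 3.
- The Follow-Up call is 3 to 5 days after dose 3, so that point lies 7 − 5 = 2 to 11 − 3 = 8 days after the call.
- It still lies inside the adverse event reporting period, which runs to 30 days after the last dose (Section 10.8.5.2.2).

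**5. Who falls between the criteria.** Remove everyone who meets one of the other three. What remains is ALT or AST above 5 and up to 8 × ULN, bilirubin at most 2 × ULN, INR at most 1.5, none of the listed symptoms, and eosinophils at most 5%.

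**The case against.** The strongest reply is that little follows. The list is advisory, and its other three criteria need no duration and can be met between doses. Section 8.1 allows stopping for an adverse event or on the physician's decision. Section 4.2 excludes subjects above 3 × ULN at Screening. Section 10.8.4 requires laboratory review and calls for repeat testing, and Section 10.10 allows unscheduled safety samples. Sections 1.2 and 3.2.4 report no safety concerns at the planned doses or at a single 320 mg dose, and nothing in the documents reports a liver signal (the Investigator's Brochure is not among them). All of this stands and keeps the weight low. It does not make the 2-week line reachable.

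Three stronger readings are tempting, and the documents do not support them.

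- **That the criterion can never act.** Section 10.9.2 does not limit it to rises after dose 1. A rise starting between the Screening sample and dose 1 could exceed 14 days by dose 3. The upper gap is also only approximate, and Section 8.3 has missed visits rescheduled.
- **That liver results go unreviewed between doses.** Section 10.8.4 requires review. What is missing is a time limit, and the laboratory manual, which might set one, is not among the documents.
- **That safety follow-up ends with the call.** Section 9.3 does say "study participation is completed once the Follow-Up Visit has been conducted", but adverse event reporting continues to 30 days after the last dose.

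It can also be said that 5 × ULN on one reading is a matter of judgment. That is fair. The plan already uses that level, however, and the line would stay a prompt to consider stopping.

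**Conclusion.** The point holds as a minor design weakness. For rises that start after dose 1, on the planned gaps, one of the four liver criteria cannot be met before the last dose. The subject described in step 5 of the working reaches dose 3 without meeting any of them. One dose per such subject is at issue. The documents give no basis for estimating how often this would happen.

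The main timing result is calendar arithmetic, confirmed by the plan's 47-day maximum. The only way round it for such a rise is gaps longer than 7 days with a very early start. The figures counted from Visit 2 Check-in also assume that the first Postdose sample is too early to show a rise. The missing review deadline is a lack of detail and carries less weight.

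The Note to File of 28 October 2022 records that enrollment was terminated after the decision of 25 August 2022. The practical use now is in any later protocol that reuses this text.

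**What to change.** **Main change.** In Section 10.9.2, delete the duration so that the second line reads ALT or AST > 5 × ULN, under the same advisory lead-in. Merge the line for values above 8 × ULN into it, since it becomes redundant.

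No new samples are needed. The cost is that an occasional subject may lose a crossover period, in a design with 4 subjects per sequence (Section 6.4), and would then fall outside the Per Protocol Set (Section 11.3). Sections 6.4 and 8 already allow the Sponsor to replace such a subject, in the same sequence.

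**Secondary clarification.** In Section 9.2, state that the previous visit's Check-in liver results are to be received and reviewed against Section 10.9.2 before the next dose, and that the visit moves within the permitted washout if they are not back. Wording that covers only results already to hand would not ensure this. No turnaround time is stated for the central laboratory, so a visit might move by up to about 7 − 3 = 4 days per washout, against the stated preference for the minimum.

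One limit remains. A rise first visible at Visit 3 Check-in would still not be caught before dose 3 unless that day's results were available before dosing.
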